3.2.2 Bladder excitation

The primary metric of successful bladder excitation will be a target evoked bladder contraction of at least 20 cmH₂O during the visit 4 cystometrogram in at least 50% of participants. Additionally, any stimulation-driven or participant-driven voiding efficiency will be calculated as

[volume voided] / [volume voided + residual measured still in bladder].

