1.3 Specific Aims

The aims of this study are to:

- **Specific Aim 1:** Use pre-implant magnetic neurography to identify and map the path of the pudendal nerve bilaterally.
- **Specific Aim 2:** Examine activation of pudendal nerve paths during unilateral stage-1 implant with pelvic floor catheters and electromyogram sensors.
- **Specific Aim 3:** Create a patient-specific model of the implanted electrode and pudendal nerve and predict stimulation-driven nerve responses.
- **Specific Aim 4:** Evaluate ability of model-derived stimulation paradigms to activate pudendal-nerve controlling bladder pathways during a cystometrogram.
- **Specific Aim 5:** Determine the change in urethral leak point pressure (ULPP) with pudendal nerve stimulation.

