1.4 Primary Outcomes

The primary outcome measure in this study are evoked bladder contractions of at least 20 centimeters of water (cmH₂O) during the stage-4 test in at least 50% of participants.

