Patients will be situated for a normal cystometrogram, in a reclining position, as shown in Figure 3 Top (from [54]) or in an upright sitting position. It is standard clinical practice to offer patients an antibiotic right before a cystometrogram. The antibiotic pill will be provided by and administered by the clinical staff. Clinical staff will insert standard urodynamic catheters into the urethra, bladder, and bowel (or vagina), and standard urodynamic EMG surface electrodes around the external anal sphincter and maybe perineal region, similar to the stage-1 procedure. Standard EMG surface electrodes may also be placed on the abdomen and/or lower back to record abdominal muscle activity. The primary urethra catheters will be a standard clinical-use Covidien Manoscan manometry catheter, to provide high-resolution urethra pressure data [50], [51], and a standard urodynamics catheter for infusing fluid into the bladder (2 urethra catheters in total). If the manometry catheter is unavailable one or two standard urodynamics catheters may be used to measure urethra pressures. Warm saline will be used to fill the bladder (~30-50 mL/min) through the bladder catheter until the participant just perceives filling. This is a standard clinical step in cystometrogram, using a standard clinical urodynamics instrument. Normal cystometrograms continue infusion until voiding (Figure 3 Bottom, from [54]), however stopping at this not-full state will allow for the assessment of stimulation effects on the bladder. Stimulation paradigms identified by the patient-specific model will be applied through the implanted neurostimulator until stimulation-driven voiding occurs or the participant expresses a very strong desire to void. At that point, the patient will be allowed to void and/or residual saline will be removed from the bladder via the bladder catheter. Approximately half of patients normally do not void around the catheter during a cystometrogram. For any participant like this,

they will have the catheters removed and will empty their bladder on to a void scale or into a toilet. This sequence will be repeated up to three times.

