At two or more time points within a cystometrogram, the urethral leak point pressure (ULPP) will be measured during Valsalva and/or forceful coughing. This will occur after infusing saline into the bladder to an intermediate volume(s) below the sensation of fullness and then pausing. Urethral leakage may not be observed; however, urethral pressures will be recorded and compared to pressures during pudendal nerve stimulation. If leakage is observed, an equal amount of saline may then be reinfused. Pudendal nerve stimulation will be turned on to a stimulation paradigm for maximum urethral sphincter activation at a comfortable level, for a maximum of a 60-second pulse train while the ULPP measurement is repeated using Valsalva and/or forceful coughing. The saline infusion will then be resumed until the participant perceives fullness and then will be stopped. Leak point pressure will again be assessed without and then with pudendal nerve stimulation as before. Each assessment of leak point pressure may be performed with stimulation on and then repeated with stimulation off, or with

stimulation off and then repeated with stimulation on. The ULPP testing may be repeated at the Investigator's discretion and participant's agreement. The ULPP measurements and stimulation-driven voiding experiments may be integrated in a fill sequence, such that both assessments may be completed at the same fullness sensation bladder volumes, using the respective stimulation parameters for each assessment.

[figure not shown]
All stimulation parameters used will be within the normal hard-coded limits of the IPG. We will not be testing new paradigms that the IPG is not capable of performing. We may vary the combination of lead contacts that are active, the pulse width of applied stimulation (i.e. duration of each pulse), the frequency of applied pulses (i.e. cycles per second), and the amplitude (i.e. volts or milliamps) of the applied stimulation. If any stimulation paradigms are perceived as uncomfortable by the participant, they will be stopped and alternate paradigms will be attempted. Once testing is completed, the IPG will be returned to the clinically-determined stimulation settings for the patient.

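### The primary outcome counts evoked bladder contractions, but visit 4 plans no quiet stimulation-off pressure recording of set length at the test volume

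*Protocol*

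**What the plan says.** Sections 1.4 and 3.2 of the protocol set the primary outcome as "evoked bladder contractions of at least 20 centimeters of water" in at least half of participants. Section 3.2.2 repeats the threshold and ties it to the target "during the visit 4 cystometrogram in at least 50% of participants". The matching aim in section 1.3 is Aim 4: "Evaluate ability of model-derived stimulation paradigms to activate pudendal-nerve controlling bladder pathways during a cystometrogram".

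Section 2.7 describes the test. The bladder is filled until the participant just perceives filling, because "stopping at this not-full state will allow for the assessment of stimulation effects on the bladder". Paradigms from the patient-specific model are then applied "until stimulation-driven voiding occurs or the participant expresses a very strong desire to void". After emptying, "This sequence will be repeated up to three times". No stimulation-off hold is described between the end of infusion and the start of stimulation, and no length is set for the stimulation period.

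For urethral leak point pressure (ULPP) at the same visit, section 2.7 plans measurements without and with stimulation. It allows either order ("Each assessment of leak point pressure may be performed with stimulation on and then repeated with stimulation off") and limits the stimulation "for a maximum of a 60-second pulse train while the ULPP measurement is repeated". Section 3.2.3 compares the two states at each volume. Section 15 notes that the study has no control arm.

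**The concern.** *Evoked* is a causal word: the contraction must be due to the stimulation. With a single group, the only available contrast is each participant's own bladder pressure with the stimulator off, under the same conditions. The plan collects mainly stimulation-on data at the test volume. The on period is open-ended, may be repeated, and by design can continue until the participant very strongly wants to void. The longer and more often a bladder is watched, the more likely an unprovoked rise of 20 cmH2O becomes.

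Such rises, counted as evoked, would push the responder share upward. They would also blur the section 3.2 comparison of bladder excitation with participant characteristics. A statistical analysis plan can define how traces are scored, but it cannot create off-state recordings that the visit never made.

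**Working it through.** **1. What off-state information the visit would yield.**

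| Possible reference | Why it is only partial |
|---|---|
| Filling trace up to first perception (section 2.7) | Volumes are lower and rising, infusion is running, and the text does not expressly say the stimulator is off during filling |
| Gap between end of infusion and start of stimulation | Right volume, but no length is set |
| ULPP off periods | Occupied by Valsalva or cough; sharing a fill with the bladder test is optional |

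None is a quiet off-state recording of known length at the test volume, and none is named as a comparator.

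**2. What limits background activity.** The fill stops short of fullness (section 2.7), and section 5.2 excludes diagnosed neurogenic bladder and other conditions affecting the micturition circuits. Both should lower the rate of spontaneous contractions. Neither gives a number.

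**3. The plan's own figure.** Section 3.1 seeks 20 completers and expects about half of those enrolled to complete: 20 / (1 − 0.5) = 40, which agrees with the stated N=40. No null rate accompanies the 50% target. With 20 completers, the target is 10 responders.

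**4. Illustration of size.** Every background rate here is assumed. Let q be the chance per fill of an unprovoked rise of at least 20 cmH2O, with no stimulation effect. Take the repetition wording as three fills.

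- Independent fills: p = 1 − (1 − q)³. At q = 0.10, p = 1 − 0.729 = 0.271.
- Within-participant correlation 0.3 (beta-binomial): s = 1/0.3 − 1 = 2.333, b = (1 − q)s, and p = 1 − [b(b+1)(b+2)] / [s(s+1)(s+2)]. At q = 0.10, b = 2.1 and p = 1 − 0.900 × 0.930 × 0.946 = 0.208.
- Chance of meeting the target with no effect: P(X ≥ 10), X binomial with n = 20 and probability p.

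| q per fill | p, correlation 0.3 | p, independent | P(X ≥ 10), correlation 0.3 | P(X ≥ 10), independent |
|---|---|---|---|---|
| 0.05 | 0.108 | 0.143 | <0.001 | <0.001 |
| 0.10 | 0.208 | 0.271 | 0.004 | 0.024 |
| 0.15 | 0.301 | 0.386 | 0.049 | 0.205 |
| 0.20 | 0.386 | 0.488 | 0.206 | 0.545 |

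With a single fill, the same chance is below 0.001 at q = 0.10 and 0.003 at q = 0.20.

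**5. Effect on the estimate.** If background and true responses are independent, an observed 50% corresponds to a true share t solving 1 − (1 − t)(1 − p) = 0.5. At q = 0.10 with three fills, t = (0.5 − 0.271)/(1 − 0.271) = 0.31 for independent fills, or (0.5 − 0.208)/(1 − 0.208) = 0.37 with correlation 0.3. With one fill it is (0.5 − 0.10)/(1 − 0.10) = 0.44. The estimate is therefore distorted at background rates where the 50% target itself is seldom met by chance.

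**The case against.** The strongest reply has four parts.

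*The fill is stopped early on purpose, and neurogenic bladder is excluded.* This stands as a limit on the background rate. It does not measure that rate, and stimulation still continues to a very strong desire to void.

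*There is already a pre-stimulation record.* A reader might infer that the bladder test has no reference at all. The documents do not support that: a large contraction on the filling trace or in the gap before stimulation would flag a participant with spontaneous activity. What is missing is a recording of set length, at the test volume, known to be off.

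*The ULPP comparison answers a different question.* This also stands. Aim 5 asks for a change in ULPP and so needs both states; Aim 4 asks about the ability to activate bladder pathways. A reader might infer that the protocol contradicts itself by controlling one outcome and not the other. It does not, and the 60-second limit is not presented as a control feature. The ULPP procedure shows only that off-state measurement is feasible at this visit.

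*The study disclaims efficacy testing* (sections 1.1 and 15), *and rules for scoring a contraction belong in the analysis plan.* The first part lowers the stakes. The second is fair for scoring rules but does not reach the recording itself, which is a visit procedure.

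**Conclusion.** The point holds: a causal primary outcome rests on open-ended, repeatable stimulation periods, without a planned quiet off recording of set length at the test volume. The direction of the possible bias is upward; its size is unknown because the documents give no background rate.

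Under the assumed rates, the 50% target is robust at 10% per fill or below (chance of false success 0.024 or less) and becomes fragile at about 15% to 20% with three fills. A reader might infer that the target could easily be met by chance. The documents do not support that, since nothing in them shows that the rate is so high. The planned data would give only a weak indication of which case applies.

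These figures rest on three fills, 20 completers, the same average background rate for all, and within-participant correlation between 0 and 0.3. Participants with detrusor underactivity may have fewer background contractions, which would lower them. This is a cheap improvement that should be made, at the low end of that grade.

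**What to change.** **Section 2.7.** In each fill, once infusion stops and before any test stimulation, record bladder pressure for a pre-set length with the stimulator off and no Valsalva or cough. Record the length of each stimulation train. Leave the end of the stimulation test as it is, and do not require stimulation-first order: stimulation ends in voiding or emptying, so a later off window at the same volume would need an interruption or a refill.

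**Section 3.2.2.** Count a contraction as evoked only if the rise of at least 20 cmH2O over the off-window baseline begins during stimulation and before permission to void. Score the off window by the same threshold. Beside the 50% figure, report:

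- the share of participants reaching 20 cmH2O in an off window;
- the contraction rate per minute, off versus on, across all paradigms applied (an equal-length first part of stimulation might cover only the first paradigm);
- the 50% figure again, without counting as responders those who reach the threshold in an off window.

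The onset rule alone does not remove spontaneous contractions that happen to start during stimulation; the off-window results show how much they could matter. With 20 completers the contrast is best treated as descriptive. An exact one-sided McNemar test at 0.025, with on and off responses independent within a participant, has power 0.69 for 50% on versus an assumed 10% off, and 0.37 for 50% versus 20%.

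**Cost.** A few more minutes per fill with catheters already in place, an occasional fill lost to an early desire to void, and a fixed off-then-on order that leaves some confounding with time.

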3.2.3 Leak Point Pressure

The ULPP will be determined as the maximum urethra pressure during any Valsalva and forceful coughing events from the urethra catheter sensors. The ULPP during pudendal nerve stimulation will be compared to the ULPP without stimulation at each volume level tested.

4. Study Recruitment

[name] will recruit patients in her clinical practice that fail conservative treatments for relevant bladder symptoms and are being considered for a pudendal nerve implant. Generally, these patients are very willing to help, as they have failed a series of prior conservative treatments and they know the pudendal implant is an off-label use. We will augment this recruitment by asking other U-M Urology clinicians to refer patients of theirs who may be candidates. Additionally, we will recruit patients from [name] practice and other Urology clinicians who have failed treatment with an implanted Interstim neurostimulator at the sacral nerve. Either [name] will perform the subject recruitment or she will introduce the patient to the study coordinator, who will then discuss the study with the patient and perform recruitment. Patient information will not be shared outside of direct clinical conversations or inquiries by the study coordinator.

As has been reported previously, patients who fail the traditional sacral nerve Interstim implant often respond positively to pudendal nerve implants [26], [61]. [name] will recruit sacral-nerve implanted patients who did not achieve clinical success to have a replacement implant at the pudendal nerve. Failed-sacral patients will be broadly recruited across clinicians within the Neurourology and Pelvic Reconstructive Surgery section at the University of Michigan Health System, which includes six Urologists who regularly see these types of patients and implant Interstim devices. Any patients not initially under [name] care who are interested in this study will be referred to her for subsequent care for receiving the IPG as well as any participation in this study. Additionally, we will also look for patients with urinary retention with detrusor underactivity and have failed bladder outlet surgery, S3 neuromodulation or a PTNS trial. These patients will be identified and referred to the study by [name] and her clinic.

Aside from the first study visit – MR imaging – all other study participation parts will be linked to standard visits as part of clinical care. This plan will help retain subjects as they will not have excessive visits in addition to their normal clinical visits. Also, our study coordinator will maintain regular contact with each participant, reminding them of appointments. As we cannot fully control the timing of participants, due to the random nature of patients seeking assistance, we will have plans in place to stagger and/or delay surgeries for participants based on study progression as long as no significant impacts on clinical care are anticipated.

5. Study Population

We will recruit 40 participants for this study. We expect that 80% of participants will be women (N=32) and 20% men (N=8), as there is about a ~4:1 rate of Interstim implantation in women versus men [62]. Within that, we anticipate 32 Caucasian (26 women; 6 men) of which two women will be Hispanic, 2 African American (women), and 6 Asian American (4 women; 2 men). We will not decline any participants based on their group membership. Within the University of Michigan local Ann Arbor area, the demographics are 73% Caucasian, 14% Asian American,

8% African American, and 5% from other groups, which we rounded off to 15% Asian American, 5% African American, and 80% Caucasian. We will target to have at least eight patients as being clinically diagnosed with detrusor underactivity (DUA), which is one of the approved indications for Interstim use. [name] has previously implanted DUA patients with Interstim at the pudendal nerve, and inclusion of a few of these patients within the study will allow us to test our ability to model and stimulate their pudendal nerve along with non-DUA patients.

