nerve-lead, and then to validate that model with patients receiving a IPG and lead that target their pudendal nerve as part of their normal clinical care. This study is not studying or establishing the efficacy of the Interstim system at the pudendal nerve. We will collect indicators of patient symptoms at the start and end of study participation to determine whether any factors relate to our ability to model and stimulate the nerve.

Figure 1 shows our overall study design, with example figures of our anticipated study progression as implemented for another neuromodulation approach by our team [30]. Further details on each step are given in Section 2 below. This NIH-funded project is part of the NIH SPARC (Stimulating Peripheral Activity to Relieve Conditions) program. A primary objective of the SPARC program is to enhance knowledge of anatomical and functional neural innervation of autonomic organs towards improved neuromodulation therapies. This project aligns perfectly with this objective, as we will use imaging and electrophysiology techniques to map a key nerve innervating pelvic organs in a relevant clinical population.

Stimulation of the pudendal nerve is also a promising minimally invasive solution for the mitigation of stress urinary incontinence (SUI). SUI is a form of incontinence in which undesired urination occurs in association with physical exertion. SUI profoundly affects quality of life [31] and is prevalent in approximately 13% of women aged 19-44 years and 22% of women aged 45-64 years [32]. There are a number of therapies and treatments for SUI [33], including conservative measures and minimally invasive options with varying and limited efficacy [34]. Pudendal nerve stimulation may help maintain urethral closure during events that cause SUI, such as coughs, however it has not been studied directly in patients. As described below, in this study we will also perform nerve stimulation during the final test visit when patients simulate conditions that cause SUI, such as with a cough. This study will examine whether nerve stimulation increases urethra pressures during these events. This study is not testing the efficacy of pudendal nerve stimulation against SUI but may provide preliminary support for a future study to examine it further.

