1.5 Secondary Outcomes

The secondary outcome measures in this study will be 1) selectivity indices for selective stimulation of pudendal nerve branches for both patient stimulation and simulated model stimulation and 2) selectivity index for selective stimulation of pudendal nerve branches for simulated model stimulation. The SI calculation may be modified in some patients, as necessary, for factors such as the presence of a short urethra that only allows for a single intraurethral pressure measure (female urethras < male urethras) and/or the placement of EMG in the perineal floor between yields one or more additional sensors. 3) Measurement of effect of pudendal nerve stimulation on urethral leak point pressure (ULPP) using stimulation targeted for the external urethral sphincter.

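### The variable called leak point pressure needs no leak, and its on/off comparison is not matched on manoeuvre, number of efforts or order

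*Protocol*

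**What the plan says.** Section 3.2.3 defines the variable: "The ULPP will be determined as the maximum urethra pressure during any Valsalva and forceful coughing events from the urethra catheter sensors". It then compares the values with and without stimulation within each bladder volume tested. Aim 5 in section 1.3 is to "Determine the change in urethral leak point pressure (ULPP) with pudendal nerve stimulation". Section 1.5 lists the same effect as the third secondary outcome, and section 3.2 calls the identification of ULPP with and without stimulation a second outcome measure.

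Section 2.7 describes the test at visit 4. On leakage it says: "Urethral leakage may not be observed; however, urethral pressures will be recorded and compared to pressures during pudendal nerve stimulation". The measurement without stimulation uses Valsalva, coughing or both. Stimulation is then switched on for at most 60 seconds "while the ULPP measurement is repeated using Valsalva and/or forceful coughing". On repeats: "The ULPP testing may be repeated at the Investigator's discretion", subject to the participant's agreement. On order, the text first describes off then on, and then allows either: "Each assessment of leak point pressure may be performed with stimulation on and then repeated with stimulation off", or the reverse.

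Section 1.1 puts the question differently: "This study will examine whether nerve stimulation increases urethra pressures during these events". It adds that efficacy against stress incontinence is not being tested and that the results might inform a later study.

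**The concern.** There are three separate problems.

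- **Label.** A leak point pressure needs a leak. The section 3.2.3 rule has no such condition, and section 2.7 foresees participants who do not leak. Even when a leak is seen, the rule takes the maximum over all events, not the pressure at the leak. The variable answers the question in section 1.1 but not the one named in Aim 5 and the secondary outcome.
- **Matching.** Bladder volume is the only factor held equal between the conditions. A maximum depends on how many efforts are made and how strong they are, and neither is fixed.
- **Order.** Either order is allowed, with no rule that balances it across participants or volumes. Fatigue, practice or a change in the bladder between the first and second measurement would then be mixed with the stimulation effect.

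The on/off difference within a participant is the whole content of Aim 5 and the third secondary outcome. If it can arise from effort, manoeuvre or order, it is weak support for a later study.

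**Working it through.** The protocol gives no effect size, SD, error rate or power for ULPP, so there is no figure to reproduce. The check is a reading of the text plus an illustration.

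**What is fixed between stimulation off and on**

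| Feature | Protocol text | Matched? |
|---|---|---|
| Bladder volume | compared within each volume (3.2.3); replacing leaked saline is optional (2.7) | yes, by design |
| Manoeuvre | Valsalva, cough or both, in each condition (2.7) | not required |
| Number of efforts | none set; repeats discretionary (2.7); a 60-second limit applies only with stimulation on | not required |
| Order | either (2.7) | not balanced |
| Leak | not needed (2.7, 3.2.3) | – |

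**Number of efforts.** Assume independent, normally distributed efforts with a common SD and no stimulation effect. The expected maximum of k efforts, in SD units, is

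E(k) = ∫ x · k · φ(x) · Φ(x)^(k−1) dx

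Numerical integration gives E(1) = 0.000, E(2) = 0.564, E(3) = 0.846 and E(4) = 1.029. The spurious difference is:

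- 1 against 2 efforts: 0.564 − 0.000 = 0.56 SD
- 2 against 3: 0.846 − 0.564 = 0.28 SD
- 2 against 4: 1.029 − 0.564 = 0.465, about 0.47 SD
- equal numbers: 0

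The condition with more efforts gets the higher value, so the sign can go either way. These shifts reach the mean in full only if the imbalance runs the same way in everyone. If 15 of 20 participants have the extra effort with stimulation on and 5 with it off, 1 against 2 efforts leaves (15 − 5)/20 × 0.564 = 0.28 SD. An even split leaves none. The mean of the efforts, unlike their maximum, has an expectation that does not depend on k.

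**Manoeuvre.** If a share s of participants uses a manoeuvre that is m SD stronger in one condition only, the mean shifts by s × m. For s from 25% to 50% and m from 0.5 to 1 SD, this runs from 0.25 × 0.5 = 0.125 SD to 0.50 × 1 = 0.50 SD.

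**Order.** Let δ be the change from first to second measurement that has nothing to do with stimulation. The on-minus-off difference contains +δ when off comes first and −δ when on comes first. With the 20 completers sought in section 3.1, the mean contains δ × (off-first − on-first)/20:

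- 20 off-first, 0 on-first: 20/20 = all of δ
- 18 and 2: 16/20 = 0.8 δ
- 15 and 5: 10/20 = 0.5 δ
- 12 and 8: 4/20 = 0.2 δ
- 10 and 10: none

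**Effect on a test, for scale only.** The protocol names no test for ULPP. In 20,000 simulated trials of 20 pairs with no true effect, a two-sided 5% paired t-test was significant in 19% when every participant made 2 efforts in one condition and 3 in the other. For 1 against 2, and for 2 against 4, the rate was 45%. With equal numbers it was about 5%. These rates assume the same imbalance in all participants and are upper illustrations, not predictions.

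**The case against.** The strongest reply is that the definition is open and fits its purpose. Section 3.2.3 says exactly what is measured, section 2.7 says that leaks may be absent, and section 1.1 asks about urethral pressures. On this view only a name is wrong, and keeping the term for observed leaks may leave few values. This is fair as far as it goes: the measurement can stay. The aim and the outcome still name something else.

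Second, section 2.7 speaks of a measurement being repeated, which describes an on/off pair, and volume is matched. A sensible investigator would use the same manoeuvre, and the SAP, which was not available, could compare like with like or average the efforts. That holds where both conditions contain the needed efforts. It does not help where a manoeuvre was done in only one condition, and no analysis plan can restore balance if nearly all participants were tested in the same order.

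Third, the sizes are assumed, and imbalances that differ in direction between participants cancel. This stands: it makes the actual bias unknown, but it does not rule it out.

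Fourth, this is a secondary outcome in a mapping study that disclaims efficacy testing. This also stands and limits the weight of the point.

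**Conclusion.** The concern holds and should be fixed. In participants without a leak, the protocol reports peak urethral pressure under stress as leak point pressure. The on/off comparison is controlled for bladder volume but not for manoeuvre, number of efforts or order.

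The defect in the text is certain; its numerical consequence is not. Under the assumptions above, unequal efforts shift the difference by 0.28 to 0.56 of an effort SD when the imbalance is the same in everyone. Between none and all of any order effect remains, depending on how orders are allocated. The direction is unknown. The harm is confined to Aim 5 and the third secondary outcome; the primary outcome is not touched.

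**What to change.** 1. **Name.** In section 3.2.3, call the variable peak urethral pressure during stress. Record leak yes or no for each assessment, and report a leak point pressure only as the pressure at an observed leak. Align sections 1.3, 1.5, 3.2 and 11.1.1.
2. **Matching.** In section 2.7, require the same manoeuvre and the same number of efforts with stimulation on and off at each volume, and make any repeat a complete on/off pair. In section 3.2.3, compare Valsalva with Valsalva and cough with cough. Equal numbers alone remove the shift from unequal efforts. A mean per effort, referenced to simultaneous bladder or abdominal pressure from the catheters already in place, would be preferable but is optional.
3. **Order.** Randomise or alternate on/off order across participants and volumes from a simple list, and record the order used.

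The cost is a few sentences and an order list, with no new equipment or visits. The investigator loses a little freedom during testing, and few participants may have a true leak point pressure to report. The change is worth most before further visit 4 data are collected. For tests already done, report the manoeuvre, number of efforts and order for each assessment as far as they were recorded.
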